## Specific Aims

Adequate access to mental health treatment is one of the highest priority problems facing the Veterans Health Administration (VHA) and VISN 19. Chronic staffing shortages exist for both psychologists and psychiatrists. Our clinical partner, VISN 19, notes that access to mental health clinics impact their performance on SAIL access and quality metrics. Poor access to care can contribute to suicide and disability, and long wait times contribute to patient dissatisfaction and disengagement from care.

Common mental health conditions are expected to remit in many cases or to be substantially improved with treatment such that patients no longer need intensive specialty mental health services. International clinical guidelines encourage the use of stepped care, in which patients should be treated at the least intensive level of care that is appropriate to their condition and VA has embraced stepped care. As part of this, VA has rolled out primary care mental health integration (PCMHI) programs at every VA. Primary care, in partnership with PCHMI, provides access to maintenance treatment (e.g., ongoing psychotropic prescriptions). VA mental health manuals encourage the transition from specialty mental health to primary care for patients whose mental health has stabilized and can be addressed in the primary care. Unfortunately, VA manuals do not provide clear guidance on which patients are appropriate for transition back to primary care or how the transition should take place. In the absence of guidance, few patients are appropriately transitioned and specialty mental health panels remain full, contributing to access problems.

To address these issues, our team partnered with VISNs 16 & 17 to pilot a demonstration project called FLOW. **This program consists of an algorithm to identify patients who are potentially appropriate for transition, a user-friendly online report to communicate this information to providers, materials to explain this process to patients and providers, and an electronic medical record (EMR) note template to document care transitions.** In cases where providers believe continued specialty mental health treatment is warranted or patients object to the transition, patients remain in specialty mental health. This approach has high acceptability to remitted patients because of perception of less stigma and reduction in appointment burden when care is managed in primary care. The FLOW program fits with VA national priorities to 'focus resources more efficiently' and 'improve timeliness of services.' To implement FLOW, external facilitators work with site-based internal facilitators and providers in specialty mental health and primary care using evidence-based implementation facilitation strategies and feeding back data to individual sites to guide implementation.

FLOW was first implemented at 4 sites in VISNs 16 and 17 and is now being implemented at all VISN 17 sites. Data from the first site indicates that 424 unique patients transitioned from specialty mental health to primary care and of those, only nine (2.1%) returned to MH after that transition, suggesting that the majority of transfers were successful. Implementation success differed dramatically across the original pilot sites but data collected did not offer an explanation for this or allow examination of implementation factors associated with success. To maximize timely access for new mental health patients, VISN 19 is embracing the FLOW program. **Given that VACO is moving towards implementing this program nationwide (personal communication from [name] in OMHSP and [name] in Office of Primary Care),** it is essential to examine the impact of this program on VA patients and clinics and understand the factors that facilitate implementation success. We are partnering with VISN 19 to evaluate this program using a **cluster-randomized stepped wedge design with 9 sites randomly allocated to receive the intervention in one of 3 steps.** This provides an ideal opportunity to conduct rigorous evaluation of FLOW's clinical impact and the implementation factors affecting success at each site.

Specific aims for this proposal, co-developed with VISN 19, are:

[figure not shown]
1. To evaluate the impact of FLOW on patient care, relative to standard care, using the evaluation framework RE-AIM, including:
  - a. Reach of the program: % of clinic patients transitioned to PC
  - b. Effectiveness: % of patients with successful transition to primary care and impact on clinic access and provider time for incoming SMH patients
  - c. Adoption: % of providers in the selected clinics transitioning patients to primary care
  - d. Implementation: use of all FLOW components, based upon the implementation checklist (see Appendix)
  - e. Maintenance: sustainment of FLOW after withdrawal of external facilitation
2. To evaluate the relationships between successful FLOW implementation and implementation factors as aligned with the Consolidated Framework for Implementation Research model (CFIR), including intervention characteristics, inner and outer context (e.g., staffing, resources, readiness to change), characteristics of individuals (e.g., leadership, facilitators and providers), and the process of implementation (e.g., the process of implementation facilitation).

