**FLOW increases access.** During implementation, 1,566 patients in participating clinics were identified as potentially meeting criteria for transition and 411 unique recovered MH patients transitioned from MH to PC. Of those, only nine (2%) returned to MH for care after the transition. The patients transitioned represented 16% of all unique patients (n=2,504) treated in the clinics implementing FLOW, suggesting that FLOW had a significant impact on workflow and access. After our team left the site, they continued using FLOW to transition a further 205 patients and independently implemented the program at a nearby CBOC. Initial data suggests that FLOW increased access and timeliness for new patients to obtain a SMH appointment (Figure 2). This increase was not due to an increase in mental health staffing, as MH FTEE per 1000 patients decreased during the initial implementation of FLOW in 2017. At 12-months post-implementation, qualitative data indicated that providers felt FLOW increased access for patients, increased communication among providers, and for SMH providers, decreased their own stress related to workload, although they reported that sometimes

the transition process was not as smooth as they would have liked. Qualitative patient interviews suggested that many patients felt ready for transition, although some were surprised by being asked to transition and recommended that patients be prepared earlier, which is incorporated in FLOW.

**Figure 2.** % patients who received a SMH appointment within 7 days of the preferred date before and after implementation of FLOW at site 1, compared with MH FTEE.

**Other sites.** FLOW is being piloted at 3 other sites in VISNs 16 and 17. Initial data suggest substantial variability in uptake of FLOW. Sites 2 and 3 have transitioned 7 and 8% of unique MH patients. At site 4, implementation is paused due to inability to enact project tasks. Substantial variation also exists in provider adoption (100% and 92% at sites 1 and 2, 33% at site 3). Sites differ significantly in readiness to implement and more work is needed to understand key barriers and facilitators to refine implementation methods.

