**Table 2. RE-AIM outcomes measured during implementation and maintenance phases (Specific Aim 1).**

RE-AIM Domain	Project Outcome	Measured by:	Level of Analysis	Timepoint
Reach	Patient transition to PC, before and after FLOW implementation	Administrative data for EMR template	Patient	Baseline; quarterly
Effectiveness	Successful patient transition to PC, defined as PCP renews psychotropic prescriptions and patient does not return to SMH within 1 year	VA administrative data for FLOW EMR template use	Patient	Baseline; quarterly in impl. phase
	Patient satisfaction with FLOW	Qual. interviews	Patient	Post-transition
	Provider satisfaction with FLOW	Qual. interviews	Provider	Post-implementation
	Impact on access, measured as (1) gain in provider hours available and (2) gain in % of	CDW Completed Appointments	Provider	Baseline; quarterly

	patients who receive appointments within 7 days of desired date	Cube		
Adoption	Providers who use FLOW for >2 patients Providers' average % of patients engaged If turnover exists, new provider use of FLOW	VA administrative data for FLOW EMR template use	Provider	Quarterly in impl. phase
Implementation	Fidelity in implementation of FLOW components	Implementation checklist	Facility	Monthly
Maintenance	Sustainment, including all RE-AI metrics Continuing facilitation activities taken over by the local facility	All metrics above Assessment of IF behavior	Patient & provider	Quarterly during maintenance phase

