Downstream effectiveness, or impact upon access, will be measured as increase in appointments within 7 days of requested date from pre-implementation to post-implementation. Data extracted from the Clinic Practice Manager suggests a fairly high baseline rate of clinic patients receive appointments within 7 days of desired date in VISN 19 (~75 to 80%). Given an average of 1000 patients per quarter per facility, a sample size of 6 clusters (24,000 patients in total) achieves 80% power to detect a difference in the percentage of patients receiving appointments within 7 days of desired date from 80% at baseline to 83% upon receiving FLOW. Power calculations are consistent with ICC values of .10, .15, .20, and .25 and would be similar to what is described above for the maintenance phase.

**Quantitative data analysis.** We will begin by describing the number of participants, providers, and sites (clusters) who were randomly assigned to each sequence and the numbers included at each quarter. Intervention conditions will initially be compared using generalized linear mixed models (HGLMs) for binary outcomes and hierarchical linear mixed models for continuous outcomes. Each model will include intervention (yes/no) and quarter as fixed predictors and models for reach, effectiveness (except for gain in provider hours), and maintenance will also include the value of the outcome during the baseline quarter as a fixed predictor. Site will be included in all models as a random effect. As we expect the intervention effect may be delayed and reach its peak at the end of the implementation period or that the effect may plateau or even decay during the maintenance period, we will also conduct a set of models where the treatment by time interaction is included as a fixed effect. Furthermore, given the sequences have different lengths of maintenance we will be able to examine whether maintenance varies with time since removal of external facilitator.

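### All-clinic reach, re-used to judge maintenance, cannot separate a shrinking pool of ready patients from loss of external facilitation

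*Combined protocol and SAP*

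**What the plan says.** Specific Aims defines Aim 1a as "Reach of the program: % of clinic patients transitioned to PC" and Aim 1e as "Maintenance: sustainment of FLOW after withdrawal of external facilitation". In Table 2 the reach outcome is "Patient transition to PC, before and after FLOW implementation", at patient level, at baseline and quarterly, with no eligible denominator. The maintenance row of Table 2 is "Sustainment, including all RE-AI metrics", together with an assessment of internal-facilitator behaviour.

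The Quantitative data analysis paragraph fits intervention and quarter as fixed effects and site as a random effect. It adds models with a treatment-by-time interaction because "the effect may plateau or even decay during the maintenance period", and states that "we will be able to examine whether maintenance varies with time since removal of external facilitator".

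On the supply of candidates, Specific Aims says that "few patients are appropriately transitioned and specialty mental health panels remain full", and Background lists staying on in specialty care as one of three options open to recovered patients. For the first pilot site, Background reports that "1,566 patients in participating clinics were identified as potentially meeting criteria for transition and 411 unique recovered MH patients transitioned". The Implementation of FLOW section counts eligible patients as feedback to the internal facilitator, but no outcome or model uses that count.

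**The concern.** A clinic that has rarely discharged recovered patients is likely to hold a stock of them. Each transition takes one out, while patients whom the provider keeps or who decline stay in the denominator. All-clinic reach is the product of two things: how many ready candidates there are, and how often a ready candidate is moved. Only the second reflects whether FLOW is being sustained. If the first shrinks, reach falls with no change in practice.

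The maintenance question is about the effect of removing the external facilitator. If reach falls in the maintenance year, the plan has no measure of transitions per available candidate with which to say why. Background says that the evaluation should inform the implementation strategy for a national rollout. Mistaking depletion for lost facilitation could bear on how much external support is thought necessary.

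**Working it through.** **1. The plan's own pilot figures (Background, first pilot site).**
- Reach: 411 / 2,504 = 16.4%, which reproduces the stated 16%.
- Flagged: 1,566 / 2,504 = 62.5% of the clinic.
- Transitioned among flagged: 411 / 1,566 = 26.2%. That leaves 1,155 (74%).
- After the further 205 transitions once the team had left: at most 616 / 1,566 = 39%. The period is not stated, so no rate can be computed.

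**2. Can the design separate the two explanations?** From Table 1, cohorts 1, 2 and 3 start in Year 1 Q2, Q3 and Q4, and each is facilitated for four quarters. In every maintenance cell, quarters on FLOW minus quarters since withdrawal equals 4. A design matrix with 3 cohort terms, 11 quarter terms and 11 categorical exposure-time terms has 25 columns and rank 25. Adding a withdrawal step gives 26 columns, and the rank stays at 25. Withdrawal is therefore aliased with a general exposure-time trend. It becomes estimable only if the trend is forced into a shape: with a linear exposure trend the matrix has full rank. From Year 1 Q4 no site is untreated, so the maintenance quarters have no concurrent control. More patients or sites on the same schedule would not change this.

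**3. How large could a fall be with no true decay?** Let P be the ready pool as a share of the clinic, h a constant chance per quarter that a ready patient is transitioned, and g the inflow per quarter:

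reach in quarter q = h × P(q); P(q+1) = P(q) − h × P(q) + g.

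h is solved so that year-1 reach equals R. With g = 0, year-2 reach divided by year-1 reach is (1 − h)^4 = 1 − R/P(1), so the fall is simply R/P(1).

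Assumptions: the 411 transitions are treated as one year's work; 62.5% is taken as the starting pool; clinic size is constant; inflow is 0 or 1% of the clinic per quarter (0.01 × 2,504 = 25 patients). The documents give none of these. The 7% reach is that of pilot site 2. The pools of 32.8% (2 × 16.4%) and 20.5% (1.25 × 16.4%) are illustrations of a ready group much smaller than the flagged group.

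| Ready pool | Year-1 reach | Fall, no inflow | Fall, 1% per quarter |
|---|---|---|---|
| 62.5% | 7% | 0.07/0.625 = 11% | 5% |
| 62.5% | 16.4% | 0.164/0.625 = 26% | 19% |
| 32.8% | 16.4% | 0.164/0.328 = 50% | 36% |
| 20.5% | 16.4% | 0.164/0.205 = 80% | 55% |

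In the second row without inflow, mean quarterly reach goes from 4.10% (16.4/4) to 3.02% (12.1/4), while the rate among ready patients stays at 7.3%.

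**4. Would one eligible denominator be enough?** Only if everyone flagged is ready. If 62.5% are flagged but 32.8% are ready, the rate among all flagged patients falls from 7.3% to 4.8% per quarter with no change in behaviour. If 20.5% are ready, it falls from 7.3% to 1.8%. The flagged group fills up with patients who will not move, so launch-eligible and newly eligible patients have to be kept apart.

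**The case against.** A reader might infer that FLOW first clears a backlog, that reach will then drop, and that a fully sustained programme will be judged not maintained. The documents do not support that.

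- The 1,566 patients were identified during implementation, not at launch, and may include people who became eligible along the way. The starting stock is never given.
- At this site, the pilot's highest in reach, 74% of flagged patients had not transitioned, and 205 more moved after the team left. Nothing says that the pool runs out.
- The pool can refill. The criteria use rolling 6- and 12-month windows, and a reluctant patient may be given a plan for a later transition.
- The analysis section allows for a delayed effect that peaks at the end of implementation, which is the opposite of early clearing.
- Maintenance is not read from reach alone. Adoption, fidelity and internal-facilitator activity are followed as well, and no reach threshold or attribution rule is set.
- Reach as a share of the population follows the plan's own RE-AIM definition.

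All of this stands, and it limits the point to what can happen. It does not remove it. Flagged is not ready, because provider judgement is final, so the 74% does not show that ready candidates remain. Fidelity and facilitator activity help to recognise abandonment, but they do not measure transitions per available candidate. Adoption, counted per provider, can itself fall when candidates are scarce.

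**Conclusion.** The point holds as a limit on how Aim 1e can be interpreted. All-clinic reach mixes the supply of candidates with the behaviour of providers, and the common four-quarter facilitated phase means that the planned models cannot separate depletion from withdrawal unless a shape is assumed. A fall can be misread; it does not follow that one will occur or that it will be misread.

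With a 62.5% pool, the fall without true decay is about 5% to 26% across the assumed reach and inflow. Larger falls, up to 80% in the cases tried, need a ready pool far smaller than the flagged group. Every figure rests on an assumed pool, an assumed inflow and a one-year reading of the pilot. The spread is itself a reason to measure the pool.

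Aim 1a is little affected: in the 62.5% pool, 16.4% reach case, 3.02% per quarter is still well above the rate of under 1% that the power section gives for facilities without FLOW.

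**What to change.** Run the existing FLOW criteria on the administrative data for each site and quarter. In the maintenance analysis, report the transition rate among eligible patients in two strata: those already eligible when FLOW started at the site, and those who first became eligible afterwards. For the second stratum, count transitions within a fixed, pre-stated window from first eligibility, so that patients who decline do not accumulate there in turn.

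State in advance that a fall in all-clinic reach will not be attributed to facilitator withdrawal unless the newly eligible rate also falls, and that both are read together with adoption, fidelity and facilitator activity. The new rate sits beside those measures and is not the sole basis for the sustainment conclusion. Keep the share of all clinic patients as the Aim 1a measure.

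The cost is some programming: the criteria already come from administrative data, and eligible counts are already produced for feedback. The newly eligible stratum is smaller, so with seven to nine sites its intervals will be wider.

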## A. Background and Significance

**Access is a priority problem.** Improving access and timeliness of services is one of the five priorities in the 2018 VA Strategic Plan. Our clinical partner, VISN 19, notes that access to mental health impacts their performance on SAIL access and quality metrics. Unfortunately, chronic staffing shortages exist in specialty mental health (SMH) and inefficiencies and poor coordination of care combine to reduce mental health access and impact wait times and frequency of visits. Poor access to care contributes to suicide and disability, and long wait times lead to patient dissatisfaction and disengagement from care.

To make the most efficient use of existing SMH providers, patients who are improved or remitted should be transitioned from intensive SMH treatment to a less intensive setting, primary care (PC). For our purposes, transition to PC is defined as an intentional, planful discharge from SMH and transfer of any prescription and monitoring responsibilities to the PCP, when the patient has sufficiently recovered such that they no longer need intensive SMH care. This will increase availability in specialty providers' panels and provide faster access for new patients referred to SMH. This approach also has high acceptability to remitted patients because of perception of less stigma and reduction in appointment burden in PC. This creates little burden on PC physicians to renew medications of patients already in their panel. VISN 19 notes that their SMH providers face barriers to transitioning patients, including lack of guidance on whom to transition, a method to identify candidates, a lack of processes and incentives to support this practice, and lack of coordination across clinics.

**Clinical Guidelines Encourage Recovery and Transition out of Mental Health.** Many mental health conditions are expected to remit. Others may be dramatically improved with evidence-based prescribing and psychotherapy, such that patients no longer need intensive SMH services. International clinical guidelines and VA practice guidelines encourage stepped care, in which patients are treated at the least intensive level of care appropriate. VA has embraced stepped care and rolled out primary care mental health integration (PCMHI) programs at every VA. Primary care, in partnership with PCHMI, provides access to maintenance treatment (e.g., ongoing psychotropic prescriptions). VA mental health manuals encourage the transition from SMH back to PC for patients who have stabilized and can be addressed in the primary care setting. Having a mechanism for transition back to PC is consistent with the VA and SAMHSA-supported Recovery Model, which facilitates recovery rather than continued dependence upon treatment. In contrast to this guidance, however, lack of a way to 'graduate' successfully sends patients the message that continued dependence upon SMH is expected.

Recently, VA's Office of Mental Health and Suicide Prevention (OMHSP) has embraced the Mental Health Continuum of Care Model (CoC; Figure 1). It incorporates stepped care, the recovery model, and measurement-based care to determine when to step up or step down in care intensity. According to OMHSP's Continuum of Care workgroup report, "Within stepped care, the basic tenet is to start with the least resource-intensive, yet likely to be effective, treatments, only 'stepping up' to more intensive/specialist services as clinically indicated and 'stepping down' once maximum clinical benefit has been obtained from the higher level of care." Further, it indicates that "discussions regarding stepping down should occur when Veterans have met their treatment goals or are stabilized as demonstrated by validated assessment of their symptoms and functioning." The processes for stepping up care are already well defined in clinical practice guidelines and policy manuals, but there is very little to determine when or how to step down. The FLOW program will assist VA providers and clinics in making this clinically important decision and implementing processes to facilitate it.

**There is no current solution for the problem of care transitions.** In the absence of processes to facilitate discharge, patients who recover and no longer need SMH are left with 3 options: 1) stay in SMH and continue attending multiple unneeded yearly visits; 2) disengage from SMH by no-showing and discontinuing medications without supervision; or 3) ask their SMH provider to transition them to PC. Given the current poor coordination, lack of agreements between SMH and PC, and lack of experience with these transitions, option 3 is unlikely to be easy or seamless. VA Central Office indicated that electronic medical record (EMR) templates for transition to PC exist in only a few facilities nationwide and are rarely used.

**The FLOW program assists facilities with transitions.** The FLOW program was created to address this need. FLOW consists of EMR-based criteria to identify patients who may be eligible for transition to PC and a user-friendly online report to communicate this information to clinicians. The criteria were developed by the FLOW team in consultation with stakeholders and a Veteran community advisory board. Current criteria are that patients must be taking three or fewer psychotropic medications, not be taking antipsychotics, lithium, or a mood stabilizer when bipolar disorder is present, had no new psychotropic medications in the past 6 months, no psychiatric inpatient or psychiatric ER visits in the past 12 months, and have no suicide risk flag. Recent refinements of these criteria added that the patient must not be taking Suboxone and must not be high risk for suicide based upon REACHVet score. Because these criteria rely upon information available in administrative databases, they may miss subjective signs that the patient is not ready for transition such as milder suicidal ideation or near-hospitalization episodes. As such, provider clinical judgment based upon the individual patient's current functioning, strengths, and resources, is the final determination of eligibility. The process of transition starts first with identification of potential eligibility via the online FLOW report. SMH providers review the list and determine which patients they believe are clinically appropriate, and discuss this with the patient at their next appointment to determine if the patient feels ready to transition. If yes, the SMH provider contacts the PCP to facilitate transition. If a patient is reluctant to transition, the SMH provider may make a plan for what level of functioning would indicate recovery sufficient to transition. FLOW materials discuss how measurement-based care can be used to guide decisions about transition and education materials for providers in SMH and PC about how to have therapeutic conversations with patients about transition. It also contains education materials for patients about the transition, how to address service-connection concerns, what to do if they have a resurgence in symptoms, and an EMR template to document transitions and facilitate communication to PCPs.

Implementation of FLOW begins with weekly meetings between the external facilitator, [name], and the identified local champion at a site. Local champions are selected by sites based upon a list of criteria including interpersonal characteristics (e.g., strong communicator) and role and tenure at an organization. The FLOW external facilitator meets with the local champion weekly to feed back data on transitions, provider adoption, transition success, process data, and to problem solve barriers that arise. VISN 19 believes that having an official channel with processes, coordination, and support for these transitions will enhance the Veteran's experience with transition to PC and encourage a focus on recovery, all while increasing access for future patient referrals to SMH (personal communication, [name], 10/5/18).

[figure not shown]
**FLOW is effective in pilot programs.** We piloted FLOW in VISN 16 and 17. The process began with meetings with leadership and provider stakeholders. Formative qualitative interviews were conducted with providers in SMH, PCMH, and PC before implementation. Qualitative data indicated that providers from all settings noted several strengths, including an increase in access to care for newly referred Veterans, less appointment burden on recovered patients, and signifying to recovered patients that they were better. Providers were concerned that PC could not offer the same level of care as SMH and that some Veterans may be reluctant to transition due to concerns about symptom reoccurrence, loss of service connection, or alliance with their SMH provider. To address these concerns, provider and patient brochures were altered where necessary to allay concerns. After multiple meetings with VISN and local facility operations partners, providers in the various clinics, and stakeholders, FLOW was implemented.

**Evaluation Framework.** Guiding the evaluation of FLOW was the Reach, Effectiveness, Adoption, Implementation, Maintenance framework (RE-AIM). RE-AIM provides a way to assess outcomes in five facets: reach, or % of the population affected by a program; effectiveness, or the impact of the program upon the patients and clinics; adoption, or the proportion of providers who use the program; implementation, whether the program was implemented as intended; and maintenance of the program over time after implementation.

**FLOW increases access.** During implementation, 1,566 patients in participating clinics were identified as potentially meeting criteria for transition and 411 unique recovered MH patients transitioned from MH to PC. Of those, only nine (2%) returned to MH for care after the transition. The patients transitioned represented 16% of all unique patients (n=2,504) treated in the clinics implementing FLOW, suggesting that FLOW had a significant impact on workflow and access. After our team left the site, they continued using FLOW to transition a further 205 patients and independently implemented the program at a nearby CBOC. Initial data suggests that FLOW increased access and timeliness for new patients to obtain a SMH appointment (Figure 2). This increase was not due to an increase in mental health staffing, as MH FTEE per 1000 patients decreased during the initial implementation of FLOW in 2017. At 12-months post-implementation, qualitative data indicated that providers felt FLOW increased access for patients, increased communication among providers, and for SMH providers, decreased their own stress related to workload, although they reported that sometimes

the transition process was not as smooth as they would have liked. Qualitative patient interviews suggested that many patients felt ready for transition, although some were surprised by being asked to transition and recommended that patients be prepared earlier, which is incorporated in FLOW.

**Figure 2.** % patients who received a SMH appointment within 7 days of the preferred date before and after implementation of FLOW at site 1, compared with MH FTEE.

**Other sites.** FLOW is being piloted at 3 other sites in VISNs 16 and 17. Initial data suggest substantial variability in uptake of FLOW. Sites 2 and 3 have transitioned 7 and 8% of unique MH patients. At site 4, implementation is paused due to inability to enact project tasks. Substantial variation also exists in provider adoption (100% and 92% at sites 1 and 2, 33% at site 3). Sites differ significantly in readiness to implement and more work is needed to understand key barriers and facilitators to refine implementation methods.

**Need for further evaluation.** FLOW has recently been disseminated to other V17 sites through a passive implementation strategy--providing sites with FLOW materials and a monthly consultation call. Of the 5 sites receiving the passive implementation strategy, 3 sites have transitioned 0 or 1 patient in the year since receiving FLOW materials, 1 site has had minimal success, whereas 1 site has achieved rates roughly similar to that in the official pilot. Given the wide variation in program success and evidence that passive implementation is generally insufficient, it is clear that successful implementation depends heavily on context, local implementation efforts, and internal facilitators. As VACO is moving towards implementing this program nationwide, it is essential to examine the impact of this program on patients and clinics and understand what facilitates implementation success. Further evaluation in a new VISN-wide setting will a) indicate effectiveness in a larger scale evaluation effort and b) allow us to understand which implementation factors are influential and provide insights that can shape the implementation strategies used in a later national rollout.

With approximately 1.8 million Veterans receiving specialty mental health care nationally (Clinic Practice Management Dashboard [CPMD], data extracted 4/18/19), a national rollout of FLOW has the potential to dramatically increase access. If sites achieve the same transition rate as in the pilot (7%), an estimated 126,000 to 288,888 patients would transition. Given that the average SMH patient has 7.5 SMH visits per year (including assessments, medication management, therapy, groups, and social work visits (CPMD, data extracted 4/18/19), this translates into nearly 1 to 1.4 million freed up appointment slots in SMH per year.

